4. ANALYSIS AND REPORTING

4.1 Final Analysis

All final, planned analyses will be performed after the last participant has completed all study assessments, all relevant study data have been processed and integrated into the analysis database, and the database has been locked.

Protocol: TNX-CY-P306 Page 12 of 36

Final v1.0

5. SAMPLE SIZE DETERMINATION

No sample size calculations were made for this study as it is a follow-on, open-label study. The sample size for this study will depend upon the number of patients who complete the lead-in study, remain eligible for entry, and indicate willingness to participate in this extension study.

Protocol: TNX-CY-P306 Page 13 of 36

Final v1.0

6. ANALYSIS POPULATIONS

The following analysis populations are planned for this study:

• Safety Population (SAFETY): All participants who receive at least 1 dose of study drug in Study TNX-CY-P306. Participants who are issued study drug, but return 100% of it (i.e., none consumed) will be excluded from the Safety Population; likewise, participants that have no follow up following receipt of study drug to indicate they took drug are excluded. All analyses will be performed using this population, unless otherwise specified in this SAP.

Protocol: TNX-CY-P306 Page 14 of 36

Final v1.0

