## 9.2. Visit 2 (Telephone Visit: Week 2)

For patients enrolled from the double-blind lead-in study, P301/HONOR only: Visit 2 will be done as a telephone call to the patient and should be conducted after 2 weeks of treatment, on Day  $14 \pm 3$  days.

The following steps should be completed:

- Assess changes in concomitant medications
- Assess study drug compliance based on patient verbal report
- Assess occurrence of AEs, including any oral AEs and whether an unscheduled visit is indicated for an examination of the oral cavity
- Review patient instructions regarding drug dosing and storage
- Administer the 'Since Last Visit' C-SSRS telephonically

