## 11.3. Serious Adverse Events (SAEs) and Serious Adverse Drug Reactions

Any SAE that occurs at any time during the study, or within 28 days after the patient's last exposure to study drug, including a clinically significantly abnormal laboratory test result that is considered serious, must be reported to Tonix or its designee(s) so that Tonix may comply with regulatory obligations. If the SAE is life-threatening or fatal, it must be reported to Tonix or its designee(s) immediately, by email or telephone. For these and all other SAEs, an SAE report form must be completed and sent by facsimile or email to Tonix or its designee(s) within 24 hours of the site's initial awareness of the event. These requirements apply equally to all patients, regardless of the study phase or the at-risk patient's treatment assignment.

A serious adverse event (experience) or reaction is any untoward medical occurrence that, at any dose:

- Results in death,
- Is life-threatening,
- Requires in-patient hospitalization or prolongation of existing hospitalization,
- Results in persistent or significant disability/incapacity,
- Is a congenital anomaly/birth defect, or
- Is an important medical event

*NOTE:* The term "life-threatening" in the definition of "serious" refers to an event in which the patient was at risk of death at the time of the event. It does not refer to an event that hypothetically might have caused death if it were more severe.

Medical and scientific judgment should be exercised in deciding whether expedited reporting is appropriate in other situations, such as important medical events that may not be immediately life-threatening or result in death or hospitalization but may jeopardize the patient or may require intervention to prevent one of the other outcomes listed in the definition above. *These should also usually be considered serious*. Examples of such events are intensive treatment in an emergency room or at home for allergic bronchospasm, blood dyscrasias or convulsions that do not result in hospitalization, or development of drug dependency or drug abuse.

A death occurring during the study or reported to the Investigator after study participation (no required post-study time limit) must be reported to Tonix or its designee(s) immediately, whether or not it is considered treatment-related. Initial SAE reports must be followed by detailed

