10.1.2 Serious Adverse Events

A summary of incidence rates (frequencies and percentages) of newly-emergent SAEs by SOC and preferred term will be prepared for the Safety Population. A data listing of all SAEs will also be provided, displaying details of the event(s) captured on the CRF.

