10.1.3 Deaths

A listing of deaths will also be provided for the Safety Population.

Protocol: TNX-CY-P306 Page 22 of 36

Final v1.0

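### The Safety Population requires evidence of intake after dispensing, so a death or incapacitating SAE with no dosing evidence from any source could be left out of the death listing, the SAE table and the long-term tables

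*SAP*

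**What the plan says.** SAP Section 6 opens with an exposure definition: "All participants who receive at least 1 dose of study drug in Study TNX-CY-P306". It then removes two kinds of patient. The first returned every tablet. The second is covered by this clause: "likewise, participants that have no follow up following receipt of study drug to indicate they took drug are excluded". The section closes by making the result the default: "All analyses will be performed using this population, unless otherwise specified in this SAP".

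Two outputs name this population directly. Section 10.1.3 says: "A listing of deaths will also be provided for the Safety Population". Section 10.1.2 says that a summary of "newly-emergent SAEs by SOC and preferred term will be prepared for the Safety Population". Section 12 also confines the analyses spanning P301, P303 and P306 to the P306 Safety Population (apart from disposition in 12.1), and the overall summary in 12.2 includes TEAEs leading to death.

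Other outputs are worded more widely. Section 10.1.2 continues: "A data listing of all SAEs will also be provided, displaying details of the event(s) captured on the CRF". Section 10.1 has the AE listings show every AE collected in P306, and Section 8.1 bases disposition on everyone with data in the database.

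Protocol 11.3 sets a wide reporting duty: "A death occurring during the study or reported to the Investigator after study participation (no required post-study time limit) must be reported". The protocol's own Safety Population (synopsis, Statistics; Section 12.1) rests on exposure alone, and a single tablet is enough. It has no follow-up condition.

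**The concern.** Membership of the Safety Population depends on information obtained after dispensing, and an early death or incapacitating event can prevent that information from being obtained. The exclusion can therefore depend on the outcome. A patient whose intake is unknown is handled like one shown to have taken nothing.

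The primary objective is long-term safety, and the protocol administers the C-SSRS at every visit. In such a study the death listing should be at least as wide as the sites' duty to report deaths. As written it can be narrower, and the omission would fall on the outputs a reader consults first for deaths and SAEs.

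Section 12 extends the effect backwards. A patient excluded for unconfirmed P306 intake also loses any TNX-102 SL exposure and TEAEs from P301 and P303. For a Track A patient who completed both, that is 12 + 12 = 24 weeks on drug.

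**Working it through.** The plan states no figure for this point, so there is none to reproduce. The check sets each output against its stated population, with simple date arithmetic.

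**1. What exclusion requires.** The patient is dispensed drug at Visit 1. The event occurs before any informative contact. No bottle count shows use, and no report or record indicates a dose. All of these must hold together. The SAP does not say whether a death report, hospital record or recovered bottle counts as follow-up.

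**2. Where such a patient would appear.**

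| Output | SAP section | Population as worded | Patient with unconfirmed intake |
|---|---|---|---|
| Death listing | 10.1.3 | Safety Population | Left out |
| Newly emergent SAE incidence table | 10.1.2 | Safety Population | Left out |
| Long-term TEAE tables, including those leading to death | 12, 12.2 | P306 Safety Population | Left out, with earlier P301/P303 data |
| SAE listing | 10.1.2 | None named | Unclear |
| AE listing | 10.1 | Every AE collected in P306 | Unclear, though the wording is wide |
| Disposition | 8.1 | Everyone with data in the database | Included |

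The two unclear rows arise because Section 6 applies its default to all analyses, and Section 10 opens by placing the safety analysis on the Safety Population. The default in Section 7.1, by contrast, speaks only of tables.

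**3. The interval before the first scheduled contact** (Protocol 9.2, 9.3 and Appendix 1, using the protocol's day count).

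- The Week 2 call is only for patients "enrolled from the double-blind lead-in study, P301/HONOR". Its latest day is 14 + 3 = Day 17.
- Patients from P303 have no such call. Their first scheduled contact is the Week 7 visit, at the latest 49 + 7 = Day 56.
- The Visit 1 supply is 3 bottles × 40 tablets = 120 tablets. At 2 per night, 120 / 2 = 60 nightly doses, so resupply does not force an earlier contact.

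**4. Whether another rule restores the patient.** SAP 11.2 assigns a missing last dose date to the day before the last attended clinic visit. Suppose that visit is Visit 1, on day d, and take the first dose as the evening of d. Duration = last − first + 1 = (d − 1) − d + 1 = 0 days. The rule does not make the patient exposed.

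**5. Agreement with the protocol.** The follow-up condition is in the SAP only. SAP Section 13 records one change from plan, the Day 0 to Day 1 renumbering, and does not mention this one.

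**The case against.** The strongest reply is that the rule reaches few patients. It requires neither a scheduled visit nor contact with the patient, only some indication of intake. A reported death generates information: Protocol 11.3 requires immediate reporting, then detailed descriptions with hospital records when requested. A partly used bottle or a hospital note could keep the patient in. This stands, and it is why the conclusion is conditional on no dosing evidence from any source. It is incomplete because the SAP does not say that such information qualifies.

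A second reply is that some indication of intake is a reasonable way to apply an exposure definition, and that presuming intake for every dispensed patient may put unexposed people in the denominator. That is fair for AE percentages, where neither default is plainly an error. It does not justify restricting a listing of deaths, which has no denominator.

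Two stronger readings are tempting and are not supported:

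- A reader might infer that the death would appear nowhere in the safety output. The SAE listing, the AE listing and disposition are worded widely enough that this does not follow. The documents support only that coverage by the two listings is unclear.
- A reader might take the overdose warnings in the appended label (Protocol Appendix 3) as the typical case. A recognised overdose of study drug is itself evidence of intake, so that patient would stay in. The label also concerns a different cyclobenzaprine product.

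**Conclusion.** The concern holds in a conditional form. The SAP's wording allows a reportable death or SAE after dispensing to be left out of the death listing, the SAE incidence table and the long-term TEAE tables when no source shows intake. The interval before the first scheduled contact runs to Day 17 for patients from P301/HONOR and Day 56 for patients from P303. Unscheduled contact may come sooner.

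The documents do not say how many patients the rule would affect, so no expected bias can be stated. At the enrolment ceiling of 200, one assumed death of this kind would be the difference between 1/200 (0.5%) and 0/199 (0%). That is a hypothetical illustration, not an expected effect: the death output is a listing, and the SAP plans no confidence interval for deaths.

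The conclusion assumes that the named populations are applied literally and that Section 6 is not read to include indirect evidence. If the sponsor already counts death reports, records and bottle counts as follow-up, the gap narrows to patients for whom those sources are silent. The change is worth making because it costs little and removes an omission that can depend on the outcome.

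**What to change.** 1. **SAP 10.1.2 and 10.1.3.** List all deaths and all SAEs for every patient dispensed study drug in P306, with a flag for unconfirmed intake. This is the essential change.
2. **SAP 6.** State that death reports, hospital records and bottle counts count as follow-up, and exclude a patient only when non-intake is shown. If the current rule is kept, add a sensitivity line for deaths and SAEs using all dispensed patients.
3. **SAP 10.1.** State whether the AE listings cover patients outside the Safety Population.
4. **SAP 13.** Record the departure from the protocol's Safety Population definition.

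The cost is SAP wording, one flag variable and possibly one extra table line. No data collection or patient management changes. The downside is that a few patients with unknown intake may enter a denominator, which could lower AE percentages slightly. The flag makes them visible, and keeping the current population with the sensitivity line avoids changing the main percentages.

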7. GENERAL ISSUES FOR STATISTICAL ANALYSIS

7.1 General Statistical Methodology

Descriptive summaries will be provided where appropriate for each of the primary and secondary variables. In general, tables will summarize data by treatment group as defined in Section 3.2 and visit.

All tables will be completed for the Safety Population unless otherwise specified.

Continuous, quantitative, variable summaries will include the number of participants (N) with non-missing values, mean, standard deviation (SD), median, minimum, and maximum.

Categorical, qualitative, variable summaries will include the frequency and percentage of participants who are in the particular category. In general, the denominator for the percentage calculation will be based upon the total number of participants in the study population for the treatment group unless otherwise specified.

Unless otherwise noted, baseline values are defined as the last non-missing measurement prior to the first dose of open-label study drug in Study TNX-CY-P306. Change from baseline will be defined as the post-baseline visit value minus the baseline value.

ET participants will only be followed if required to monitor an on-going adverse event or other condition.

Participants are not supposed to change study sites; however, should this be necessary to allow a participant to continue in the study, participants will be analyzed under the site where they were initially enrolled.

Study day after first dose is defined as assessment date – first dose date +1. Dates prior to first dose are defined as assessment date – first dose date. Note that the protocol refers to "Day 0"; for the purposes of the datasets and analyses, this would appear as day 1.

All analyses will be performed using Statistical Analysis System (SAS®) Software version 9.4 or later.

Unless otherwise noted, 95% confidence intervals will be presented for statistical tests.

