#### **Safety Analyses:**

Safety data will be summarized as a single treatment group receiving 1 or more doses of TNX-102 SL 5.6 mg. Adverse events will be coded using the same version of the Medical Dictionary for Regulatory Activities (MedDRA) as used for the lead-in HONOR study and will be summarized overall and by preferred term and system organ class (SOC). Adverse events will also be summarized by severity and relationship to study drug. Serious AEs and AEs leading to discontinuation of study drug will also be summarized. Adverse events that are ongoing in the 12-week open-label extension study P303 or the lead-in double blind HONOR study will be transcribed into the eCRF. All other adverse events that are reported after starting TNX-102 SL in this extension study, or that worsen after entry into this extension study, will be considered newly emergent AEs (NEAEs), even if the type of event was previously reported (and resolved) during either the HONOR study or the 12-week open-label extension study.

Actual values and change from baseline for clinical laboratory test results, vital sign measurements, depression status via the BDI-II and PTSD symptom status via the PCL-S, will be summarized at endpoint using descriptive statistics (n, mean, SD, median, minimum, and maximum). The number of

<sup>1 Tonmya is the FDA conditionally accepted proposed proprietary name for TNX-102 SL for the treatment of PTSD.

patients with baseline and treatment-emergent suicidal ideation and/or suicidal behavior or self-injurious behavior, based on the C-SSRS, will be summarized by treatment group.

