# 12.1. Evaluation of Safety

Safety data will be summarized as a single treatment group receiving 1 or more doses of TNX-102 SL (patients that have taken only 1 tablet of TNX-102 SL will be included).

Safety will be assessed by the monitoring and recording of AEs, clinical laboratory tests, vital signs, visual examination of the oral cavity findings, the monitoring of suicidality using the Columbia C-SSRS scale, and patient-rated assessments of depressive symptomology (BDI-II) and PTSD symptomology (PCL-S).

AEs will be coded using the MedDRA and will be summarized overall and by preferred term and SOC. AEs will also be summarized by severity and relationship to study drug. SAEs and AEs leading to discontinuation of study drug will also be summarized.

Actual values and changes from the extension study baseline values for clinical laboratory test results and vital sign measurements will be summarized at endpoint using descriptive statistics (n, mean, standard deviation (SD), median, minimum, and maximum). Laboratory values will be displayed in the data listings along with corresponding normal ranges, and those that are outside the normal range will be flagged.

Based on the C-SSRS results, the frequency and severity of suicidal ideation and behavior will be tabulated at each time point. The number of patients with baseline and treatment-emergent suicidal ideation and/or suicidal behavior or self-injurious behavior, based on the C-SSRS, will be summarized by treatment group.

All data gathered will be listed by patient and parameter, and clinically significant abnormalities should be recorded as AEs. AEs of special interest indicating potential abuse and dependency will be evaluated and summarized as described in the Statistical Analysis Plan.

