2. STUDY OBJECTIVES AND ENDPOINTS

2.1 Study Objectives

2.1.1 Primary Objective

The primary objective of the study is to evaluate the long-term safety of TNX-102 SL taken daily at bedtime over an additional 40 to 52 weeks in patients with PTSD who have participated in a double-blind lead-in HONOR study (TNX-CY-P301) and possibly a 12-week open-label extension study TNX-CY-P303.

Protocol: TNX-CY-P306 Page 9 of 36

Final v1.0

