3.2 Method of Treatment Assignment and Randomization

All patients will be assigned to TNX-102 SL, 5.6 mg regardless of which treatment arm they were randomized to in the lead-in study. No patients or site personnel will know what the prior treatment was in the double-blind lead-in study.

Throughout this document, when describing analyses performed by treatment group, this will refer to the treatment that the subject was randomized to in the double-blind lead-in study.

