8. STUDY PARTICIPANTS AND DEMOGRAPHICS

8.1 Disposition of Participants and Withdrawals

The numbers and percentage of participants entering, completing the study, and withdrawing from the study, along with reasons for withdrawal, will be tabulated overall and by treatment group. This summary will be based on all participants who have data entered into the database.

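### The protocol summarises safety as one TNX-102 SL group, but the SAP's default splits P306 safety tables by lead-in arm, specifies a total only for disposition, and does not declare the difference

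*SAP*

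**What the plan says.** The protocol gives the same instruction twice. Section 12.1 reads: "Safety data will be summarized as a single treatment group receiving 1 or more doses of TNX-102 SL". The synopsis, under Safety Analyses, repeats it with the dose: "Safety data will be summarized as a single treatment group receiving 1 or more doses of TNX-102 SL 5.6 mg". Section 12.1 also says of suicidality that results "based on the C-SSRS, will be summarized by treatment group", without defining any groups by lead-in arm.

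The SAP gives the phrase treatment group a specific meaning. Under 3.2, wherever analyses are described by treatment group, "this will refer to the treatment that the subject was randomized to in the double-blind lead-in study". Section 7.1 then sets the general layout ("In general, tables will summarize data by treatment group as defined in Section 3.2 and visit") and the general percentage denominator ("based upon the total number of participants in the study population for the treatment group unless otherwise specified").

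In the P306-only sections, an across-arm total is written down for disposition, where numbers "will be tabulated overall and by treatment group" (SAP 8.1). SAP 13, which lists changes from the planned analysis, mentions only the numbering of study days.

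**The concern.** P306 has one treatment. The primary objective is to "evaluate the long-term safety of TNX-102 SL taken daily at bedtime over an additional 40 to 52 weeks in patients with PTSD", so the natural unit of reporting is everyone who took the drug in P306. The SAP's default instead uses an assignment from an earlier study as the column and the denominator. If the tables are built as 7.1 is written, the safety results specific to P306 appear in two parts, with no specified table for the whole exposed group. A reader of the study report would not learn from SAP 13 that the protocol's single-group presentation had been replaced.

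**Working it through.** The plan states no sample-size calculation or precision target for safety, so there is no figure to reproduce. The check is a comparison of the text, followed by a small illustration.

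**1. Layout by type of result**

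| Result | P306-only layout in the SAP | Single-group result in SAP 12 |
|---|---|---|
| Disposition | Overall and by arm (8.1) | Yes, by treatment sequence and overall (12.1) |
| Adverse events | No columns stated in 10.1, so the 7.1 default applies | Yes, but treatment-emergent events over three studies (12.2) |
| Laboratory | No columns stated in 10.2; by visit, with 95% CIs; 7.1 default | Minimum, maximum and final values, shifts, liver categories (12.4) |
| Vital signs | No columns stated in 10.4; by time point, with 95% CIs; 7.1 default | Minimum, maximum and final values, notable values (12.3) |
| C-SSRS | By treatment group (10.3) | None |
| BDI-II | Listed in Section 10 without a layout; 9.1.1 compares the arms | None |

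**2. Why SAP 12 does not replace a P306 total**

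- *Period.* For patients given TNX-102 SL in P301, Section 12 counts events from the start of P301. It does not isolate the P306 treatment period.
- *Recurrence.* The interval tables in 12.2 run from the first active dose in any study and, where a patient has several events in a category, keep the first. Read literally, an event seen in P301 that recurs in P306 could drop out of the later interval. The protocol synopsis treats such a recurrence as newly emergent.
- *Baseline.* Sections 12.3 and 12.4 measure change from the last value before the first ever TNX-102 SL dose. Section 10 uses the P306 baseline defined in 7.1. The two differ for anyone who took TNX-102 SL before P306.

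**3. What can be recovered from two arm columns**

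Each patient belongs to one arm, so pooled incidence is (x1 + x2)/(N1 + N2). A pooled mean is (n1·m1 + n2·m2)/(n1 + n2), and a pooled SD follows from the arm sizes, means and SDs. A reader could therefore rebuild a confidence interval for a mean change, but it would not be displayed. A pooled median cannot be rebuilt from two arm medians.

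**4. Illustration of precision**

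Inputs: the enrolment maximum of 200 (protocol 6.2), and an arm split that the documents do not give and is therefore assumed. With zero events in n patients, the one-sided 95% upper bound is 1 − 0.05^(1/n). The chance of seeing at least one event of true incidence 1% is 1 − 0.99^n.

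| n | Upper bound, zero events | Chance of at least one event at 1% |
|---|---|---|
| 200 (pooled) | 1.49% | 86.6% |
| 100 (each arm, 100:100) | 2.95% | 63.4% |
| 133 (larger arm, 133:67) | 2.23% | 73.7% |
| 67 (smaller arm, 133:67) | 4.37% | 49.0% |

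For the planned 95% CIs on laboratory and vital-sign changes, width goes roughly with 1/√n. At an equal split and the same SD, each arm's interval is about √(200/100) = 1.41 times as wide as the pooled one.

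**The case against.** The best reply is that a pooled long-term safety analysis is already planned. SAP 12 covers the P306 Safety Population, is restricted to TNX-102 SL, and exists to support the long-term safety profile. The synopsis looks for at least 52 weeks of exposure in at least 50 patients. Track A patients receive only 40 weeks in P306, so for them only cross-study data can reach that mark. P306 events also feed the Section 12 tables at full N. This stands: a reader might infer that the primary objective is left without pooled evidence, and the documents do not support that.

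Second, 7.1 says what is done in general, and 10.1, 10.2 and 10.4 do not themselves split by arm. A total column is therefore unspecified, not ruled out. This also stands. But those sections name no columns of their own, so 7.1 is the only layout rule a programmer has.

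Third, pooled counts are simple sums of arm counts. That is true for incidence, but not for medians.

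Fourth, the protocol itself uses by treatment group for C-SSRS. Its meaning in a single-treatment study is unclear, so C-SSRS is not a clean departure from a pooled instruction. Even so, under the SAP's definition the phrase becomes a split by lead-in arm, and Section 12 has no C-SSRS result to offset it.

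**Conclusion.** The protocol and SAP disagree on how P306 safety is presented, and the disagreement is undeclared. What goes unspecified is limited: a pooled P306-period summary of newly emergent adverse events, of C-SSRS and BDI-II, and of by-visit laboratory and vital-sign changes from the P306 baseline with their 95% CIs. The first could be summed by hand. Pooled medians would be missing, and pooled CIs would not appear as displayed results.

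Two stronger readings should be resisted. A reader might infer that events on active drug will be headed placebo. The SAP gives no column headings, and 9.1.1 and 9.1.2 describe the groups by whether TNX-102 SL was received in a prior study. A reader might also infer that the plan doubles its upper bound for rare events. The SAP plans no such bound, and 1.5% against 3.0% rests on an assumed 200 patients and equal split. It shows the scale of the precision given up in an arm-only display; no planned estimate changes. The point is worth correcting because it touches the primary objective and is cheap to cure.

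**What to change.** Add to SAP 7.1, and repeat at the head of Section 10, that every P306 safety table shows total TNX-102 SL as the main column, with its own denominator, median and confidence interval where those are planned. Keep lead-in arm as a secondary breakdown, labelled prior TNX-102 SL and no prior TNX-102 SL, and state that prior refers to P301. Some patients given placebo in P301 may have taken open-label TNX-102 SL in P303. Name C-SSRS and BDI-II explicitly, since Section 12 does not cover them. If the sponsor prefers the arm-only layout, list it in SAP 13 as a change from protocol 12.1, with the reason.

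The cost is a sentence or two in the SAP and one extra column per table. No new data or modelling is needed.
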